## MRI Analysis

We will incorporate axonal density from NODDI analysis of multishell diffusion MRI as an advanced microstructural imaging biomarker of both acute DAI and long-term white matter degeneration. Axonal density, measured as the neurite density index (NDI) of white matter from NODDI, is a metric of the intracellular volume fraction and is not affected by changes in the free water fraction. Therefore, it is a more specific biomarker of axonal loss than any DTI metric such as FA, MD, AD, or RD. In addition, we will incorporate a quantitative imaging biomarker of MVI, specifically, CBF using ASL perfusion MRI.

#### MRI Statistical Considerations

We will calculate Pearson's correlation of each of the baseline early (<6 hours to 1 week) blood-based biomarkers, with the corresponding MRI markers that look promising based on Phase 1 results. There will be no adjustment for multiple comparisons as these comparisons are exploratory given the paucity of information about the time-course of these markers in people with TBI. ROC analysis will be performed to determine the discriminative ability of the blood-based and imaging biomarkers in predicting outcomes. AUC will be calculated and reported along with 95% confidence intervals. Prediction increment will be measured by change in AUCs calculated based on logistic regression models.

Adequacy of sample size: With 50 participants, using correlation power analysis, we have at least 80% power to detect a correlation of .38 or greater.

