# 2. TRACK-TBI PRECISION MEDICINE RATIONALE, SPECIFIC AIMS, AND OBJECTIVES FROM THE ORIGINAL GRANT SUBMISSION

#### 2.1 Rationale

In Phase I of this study, we will assess putative blood-based and neuroimaging biomarkers for DAI, MVI, and neuroinflammation (**Table 1**). Fluid biomarkers complement imaging markers and may provide important tools for precision medicine clinical trials. In Phase 2 of this study, we will collect acute data (early and ultra-early i.e., hours-days following injury), to validate the utility of these biomarkers identified during Phase I in defining TBI mechanistic endophenotypes for use in clinical trials.

**Table 1.** Proposed TBI Biomarkers and their Relationship to TBI Mechanistic Endophenotypes

Mechanistic Endophenotype	Blood-Based Biomarkers	Neuroimaging Biomarkers
Axonal injury	pNF-H, NF-L, Tau, P-Tau	MRI (DW, DTI, rs-fMRI)
Microvascular injury	vWF, c-fibronectin, ICAM-1, VCAM-1	MRI (SWI; ASL perfusion)
Neuroinflammation	IL-6, IL-10, IL-17, TNFa, HMGB-1 AutoAb[GFAP]-IgM, IgG	MRI (free water imaging) - (FISO) from NODDI
Neuronal Injury	UCH-L1	(as benchmark in Aims 2-3)
Astroglial Injury	GFAP	(as benchmark in Aims 2-3)

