## 4.2 Inclusion/Exclusion Criteria

**Table 3** summarizes study inclusion and exclusion criteria. These criteria are informed by the experience of the TRACK-TBI U01 study, and are designed to mirror criteria appropriate for future trials of neuroprotective or neurorestorative therapies. These clinical and imaging criteria were identified through the TRACK-TBI U01 study, and include select subjects with TBI who are at high risk for incomplete recovery (GOSE < 8) out to 6 months after injury. The criteria also exclude participants with very severe TBI who stand a low chance of survival.

Table 3. Enrollment Inclusion and Exclusion Criteria					
Criteria	Data Source	Comments			
Inclusion Criteria					
1. Age 18 – 65y inclusive	Chart, Interview				
2. History or evidence of TBI, according to DoD-VA criteria	Chart, Interview				
3. GCS 3 – 15 after resuscitation in the ED	Chart				
4. Cranial CT with evidence of trauma-related abnormality (i.e.,	Chart	Based on			
CT positive except for isolated epidural hematoma (EDH))		radiologist's read			
5. Ability to undergo MRI	Chart, Interview				
6. Ability to obtain informed consent from participant or LAR	Interview				
7. Fluency in English or Spanish	Interview	Based on test battery and available personnel			
Exclusion Criteria					
1. Unstable respiratory or hemodynamic status	Chart				
2. Evidence of penetrating brain injury	Chart				
3. Isolated EDH as only trauma-related CT abnormality	Chart	Favorable natural history			
4. Systemic traumatic injury that would preclude participation in study, which is expected to result in long-term disability not related to TBI	Chart				
5. Evidence of serious infectious complications (sepsis,	Chart				
bacteremia, multilobar pneumonia)  6. Acute ischemic heart disease (myocardial infarction or	Chart, Interview				
unstable angina)	Chart Internation				
7. History of syncope or hypotension	Chart, Interview	The second a least to test con-			
8. SBP < 90 mm Hg, DBP < 40 mm Hg for longer than 5minutes	Chart	Hypoxic brain injury has very poor prognosis			
9. History or evidence of active malignancy	Chart, Interview				
10. History of pre-existing neurologic disorder, such as dementia, mild cognitive impairment, uncontrolled epilepsy, multiple sclerosis, strokes, brain tumors, prior severe TBI, or other disorder that may confound interpretation of MRI or neuropsychological results	Chart, Interview	May confound interpretation of MRI or neuropsychological results			

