#### **7 SUBJECT PROCEDURES BY CORE**

#### 7.1 Clinical

The following broad categories of clinical data variable types will be collected from all enrolled patients through medical record and personal interview:

- Baseline demographics e.g., age, gender, race, ethnicity, handedness
- Baseline socioeconomics e.g., education, employment, living situation, types of support
- Baseline medical history by system including substance abuse, prior TBI, and medications
- Mechanism of injury, location, and surrounding circumstances
- Pre-hospital clinical course variables e.g., vital signs, transport times, GCS score
- Brain CT report including presence of skull fracture and intracranial abnormalities
- Emergency department clinical course e.g., vital signs, GCS, fluids, labs, toxicology, complications
- Hospital admission clinical course e.g., complications, surgeries, neuromonitoring

- Hospital daily therapeutic intensity level for ICU patients with neuromonitoring
- Admit and discharge dates and times throughout full clinical course
- Abbreviated Injury Scale (AIS) score and Injury Severity Score (ISS)
- Discharge destination and acute care outcome evaluation

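### The blood-MRI analysis is a Pearson correlation with no covariate in a cohort aged 18-65, so a correlation may partly reflect age; an age-adjusted partial correlation should stand beside it

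*Protocol*

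**What the plan says.** The protocol's paragraph on MRI Statistical Considerations (section 7.3) sets the blood-MRI analysis: "We will calculate Pearson's correlation of each of the baseline early" blood markers against "blood-based biomarkers, with the corresponding MRI markers that look promising based on Phase 1 results". It attaches no covariate, partial correlation or stratification to this analysis. Logistic regression appears in the same paragraph only for the increment in AUC when predicting outcome.

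The same paragraph says "There will be no adjustment for multiple comparisons as these comparisons are exploratory", and gives the sample-size statement: "With 50 participants, using correlation power analysis, we have at least 80% power to detect a correlation of .38 or greater".

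Three other places bear on the point:

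- **Aim.** Sections 2.2 and 2.3 aim to validate markers of diffuse axonal injury, microvascular injury and neuroinflammation. Table 1 (section 2.1) assigns markers to mechanisms, for example "vWF, c-fibronectin, ICAM-1, VCAM-1" to microvascular injury.
- **Eligibility.** Sections 4.1 and 4.2 admit ages 18 to 65 inclusive. Injury outside the head is a reason for exclusion under this criterion: "Systemic traumatic injury that would preclude participation in study, which is expected to result in long-term disability not related to TBI".
- **Data.** Section 7.1 collects "Baseline demographics e.g., age, gender, race, ethnicity, handedness", and also AIS and ISS.

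**The concern.** A correlation between a blood marker and an MRI measure supports a shared brain-injury mechanism only if obvious common causes have been considered. Age is the plainest candidate left open. It varies over 47 years in this cohort, it could relate to both sides of a pair, and it is not part of the mechanism being validated. A Pearson coefficient alone cannot separate a pair that moves together because of injury from a pair that moves together because older patients differ on both.

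The protocol already reasons this way elsewhere. Table 3 excludes pre-existing neurologic disorders because they may confound MRI interpretation. That restriction does not deal with age itself.

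At stake is how the results are read: a pair could be put forward as validated, and carried into the planned trial work, on a correlation that is partly an age effect.

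**Working it through.** **Inputs.** From the protocol: n = 50; target r = .38 with at least 80% power; 80% follow-up target in section 3.4 (.80 × 50 = 40). Assumed: alpha .05 two-sided, which the protocol does not state; and the correlation of age with each marker, for which the protocol gives nothing, so a range of .2 to .5 is shown.

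**1. The plan's own figure.** With k covariates removed, power by Fisher's z is Φ(atanh(r)·√(n − 3 − k) − 1.96). For r = .38, n = 50, k = 0: atanh(.38) = .400; .400 × √47 = 2.743; Φ(2.743 − 1.96) = 78.3%. Simulation of the t-test gives 79.2%. The stated figure is therefore essentially reproduced, though at least 80% is slightly generous. That is not the point here.

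**2. Correlation induced by age alone.** If age correlates a with the blood marker and b with the MRI measure, and nothing else links them, the Pearson correlation is a × b. The chance of p < .05 is Φ(atanh(ab)·√47 − 1.96) + Φ(−atanh(ab)·√47 − 1.96).

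| a = b (assumed) | induced r | chance of p < .05, n = 50 |
|---|---|---|
| .2 | .04 | 5.9% |
| .3 | .09 | 9.5% |
| .4 | .16 | 19.8% |
| .5 | .25 | 41.7% |

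The product is what matters, so unequal strengths can leave little: a = .5 with b = .1 gives r = .05 and about 6%.

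**3. The plan's target correlation after adjustment.** With a = b = c, the partial correlation is (r − c²)/(1 − c²). A Pearson coefficient of .38 becomes:

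- c = .3: (.38 − .09)/.91 = .32
- c = .4: (.38 − .16)/.84 = .26
- c = .5: (.38 − .25)/.75 = .17

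**4. Cost of adjusting.** The smallest correlation detectable with 80% power is tanh((1.96 + .842)/√(n − 3 − k)).

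| covariates k | n = 50 | n = 40 |
|---|---|---|
| 0 | .387 | .431 |
| 1 (age) | .391 | .436 |
| 2 (age, non-head AIS) | .395 | .441 |

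At n = 50, power for r = .38 goes from 78.3% (k = 0) to 77.4% (k = 1) and 76.5% (k = 2).

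**The case against.** The strongest reply is that this is a short paragraph in a protocol. It does not say that the coefficient is the only one to be reported, nothing in it prevents an adjusted analysis, and covariates are often left to a statistical analysis plan, which may exist. That is fair, and it is why the point is a modest one. It still stands, because the protocol does name its estimator, and that estimator does not by itself separate a shared mechanism from shared age.

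A second reply is that the work is exploratory. The protocol uses that label to justify making no multiplicity correction. It does not address a common cause.

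A third reply stands in full: the documents do not show that age relates to any of these markers, or how strongly. At .2 per side the effect is close to nominal. The exclusions for neurologic disease, malignancy, chronic heart or renal failure and serious infection may also remove some age-related variation. In addition, only a subset of the Table 1 blood markers will be assayed (section 7.2, Analysis).

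A reader might go further and infer that injury outside the head drives both sides as well, so that every mechanism claim should rest on a coefficient adjusted for age and extracranial injury. The documents do not support that. They give no route from extracranial injury to the brain MRI measure. Several exclusions, including unstable respiratory or hemodynamic status and sustained low blood pressure, may already remove some severe polytrauma. Body and brain injury can also share impact energy, so adjusting for the one may remove true signal from the other.

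**Conclusion.** The point holds in a limited form. The planned blood-MRI analysis has no age adjustment in a cohort where age varies widely, and the aim is to validate markers of specific mechanisms. A correlation may therefore partly reflect age.

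The size is unknown. Under equal assumed correlations of .2 to .5 on both sides and no direct link, the chance of a nominally significant result at n = 50 runs from about 6% to 42%, against a nominal 5%. The top of that range needs .5 on both sides, which nothing in the documents establishes. It would be wrong to read this as showing that the planned correlations are spurious, or that the power statement is in error because of it. The change is worth making because it costs almost nothing and answers a question that the Pearson coefficient cannot.

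**What to change.** 1. Beside each Pearson coefficient, report the partial correlation adjusted for age, with its confidence interval.
2. State that a blood-MRI pair will be described as supporting a shared mechanism only if the association persists after age adjustment.
3. As a sensitivity analysis only, adjust also for the highest non-head AIS score. Do not use total ISS, which can include the head region, or GCS, because either could remove the brain-injury signal itself. Say in the report that even non-head AIS may take out some true signal. Section 7.1 does not say that AIS is recorded by body region, so confirm that it is.

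Cost: one degree of freedom for age, two in the sensitivity analysis, and a few lines of code. Age is already collected, and no new visits, data or change in sample size are needed for the main adjustment. The loss of precision is the small shift shown in step 4 of the working.

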#### 1. ORIGINAL TRACK-TBI PRECISION MEDICINE GRANT SUBMISSION BACKGROUND AND STUDY OVERVIEW

Effective treatment of traumatic brain injury (TBI) remains one of the greatest unmet needs in public health. According to a 2006 publication, each year in the United States, at least 1.7 million people suffer TBI; it is a contributing factor in a third of all injury-related US deaths. An estimated 3.2 to 5.3 million people live with the long-term physical, cognitive, and psychological health disabilities of TBI, with annual direct and indirect costs estimated at over \$60 billion. More recent publications have reported an increase in these numbers. Recent efforts have increased our understanding of the pathophysiology of TBI; however, these advances have failed to translate into a single successful clinical trial or treatment. These failures are largely attributable to the fact that TBI classification approaches are blunt and have not changed in more than 3 decades. TBI patients are divided into the crude categories of "mild", "moderate", and "severe", using the Glasgow Coma Scale (GCS)3, and functional outcome is measured using the equally crude Glasgow Outcome Scale-Extended (GOSE).4 These symptoms-based categories do not permit mechanistic targeting for clinical trials. Clinical research has also been underpowered, hampered by lack of data standardization, and with limited multidisciplinary collaboration. Workshops coordinated by the National Institute of Neurological Disorders and Stroke (NINDS), Department of Defense (DOD), and the National Institute on Disability, Independent Living, and Rehabilitation Research (NIDILRR) since 2007 identified the urgent need for improved TBI classification using more accurate diagnostic and outcome tools (beyond the GCS and GOSE), along with a standardized approach to data collection. A multidisciplinary effort was launched to develop TBI Common Data Elements (TBI-CDEs). Domains included clinical data, imaging, biospecimens, and outcomes.

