## 3.2 Participants

Subjects will be recruited among patients with TBI admitted to the emergency department, trauma, or neurosurgical services at 5 participating TRACK-TBI Clinical Sites. Each site has a system for identification and early notification of potential patients who qualify for the study. The early notification system will result in timely arrival of the study coordinator or other trained study personnel, who will evaluate a participant's eligibility. Individuals notifying study personnel of potential patients may include ambulance coordinating system personnel, neurosurgery residents, emergency room physicians, or other hospital personnel who are likely to see brain injured patients shortly after their arrival.

Once notified, study personnel will review the potential patient's information and screen the patient according to the study inclusion and exclusion criteria (Table 3). Upon determining that the patient is potentially eligible for the study, consent will be obtained from the patient or the legally authorized representative (LAR) according to local IRB guidelines. If the patient is determined to have capacity to provide his or her own consent, the patient will be asked to provide informed consent. For participants whose LAR originally gave consent, an informed consent will be obtained from the participant once they have the capacity to do so. The target enrollment for this study is 50 participants.

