## 9.3 Measures of Daily/Global Function

## Functional Status Exam (FSE)

The FSE measures change in functional status specifically due to traumatic injury. The measure can be administered in relation to changes due to TBI only or both the changes associated with TBI and peripheral injuries. This measure covers 7 areas of functioning: personal care, ambulation, mobility, major activities (i.e.,

work, school), home management, leisure and recreation and social integration. These areas are evaluated using the concept of dependency to operationally define outcome at four levels. The first level signifies no change, the second level signifies difficulty in performing the activity although the person is still independent, the third level signifies dependence on others some of the time, and the fourth level signifies non-performance or inability to perform the activity or total dependence on others. A total score is generated by summing scores from the 7 categories, yielding a range from 0 (return to pre-injury baseline in all areas) to 21 (total dependence on others or can no longer perform any activities across functional areas). Persons who die are assigned a total score of 22. This measure will also be collected from the surrogate. The FSE measure should be administered by telephone but can also be administered in-person if permitted by local policy and acceptable to the subject or LAR.

Additional information regarding the administration of the FSE can be found in the pdf "Functional Status Examination Manual" saved on the Study Shared BOX folder at "Box\TRACK-TBI Precision Medicine Study Documents\Outcomes Core\Outcomes training and administration guidance".

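### The only marker-outcome analyses named, AUC and change in AUC, imply splitting graded outcomes such as the GOSE and FSE in two; a full-scale analysis should be added alongside them

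*Protocol*

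**What the plan says.** Protocol section 7.3, under MRI Statistical Considerations, sets out three analyses.

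- Pearson correlation, for early blood markers against the corresponding MRI markers.
- ROC analysis, for markers against outcome: "ROC analysis will be performed to determine the discriminative ability of the blood-based and imaging biomarkers in predicting outcomes". The reporting is also fixed: "AUC will be calculated and reported along with 95% confidence intervals".
- Added value of a marker: "Prediction increment will be measured by change in AUCs calculated based on logistic regression models".

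No other marker-outcome analysis appears in the protocol. The paragraph does not say which outcome enters the ROC and logistic models, at which visit, or at what cut.

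The outcomes collected are mostly graded. For the FSE (section 9.3), "A total score is generated by summing scores from the 7 categories, yielding a range from 0" to 21, and a participant who dies is given 22. The GOSE is a multi-level scale, and most of the batteries in sections 8.2 and 8.3 consists of scores. The only GOSE threshold in the document is in the eligibility rationale of section 4.2, which describes participants "at high risk for incomplete recovery (GOSE < 8) out to 6 months after injury". It is not presented as an analysis cut.

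On size, section 3.2 says "The target enrollment for this study is 50 participants", and section 7.3 says "With 50 participants, using correlation power analysis, we have at least 80% power to detect a correlation of .38 or greater". Section 3.4 sets an 80% follow-up target at 3 months.

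**The concern.** An AUC and a logistic model, in their usual form, compare two classes. Used on the GOSE or the FSE total, they treat everyone on the same side of the cut as equal: a participant just on the bad side counts the same as one who died, and gradations within each side are lost. The lost information cannot be recovered by choosing the cut well. A later analysis plan that names a cut would settle which split is used, but not the cost of splitting.

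This matters because Aim 2 (section 2.2) asks whether the markers can serve as predictive biomarkers, so relating markers to outcome is central to the study. With 50 participants, or about 40 followed to 3 months, there is little information to spare. A marker with a moderate relation to outcome could be passed over because of how the outcome was coded.

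**Working it through.** **Inputs.** N = 50 (section 3.2); 0.80 × 50 = 40 at the follow-up target (section 3.4); r = 0.38 (section 7.3). Three inputs are assumptions: two-sided 5%, in line with the 95% intervals; a bivariate normal latent scale for marker and outcome; and r = 0.38 applied to marker against outcome.

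**1. The plan's own figure.** By Fisher z, power = Φ(atanh(r)·√(N − 3) − 1.96).

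- atanh(0.38) = 0.400 and √47 = 6.856; the product is 2.743. Power = Φ(0.783) = 78.3%.
- A simulated t-test of Pearson's r (20,000 runs) gives 79.1%.
- Fisher z needs r = 0.388 for a full 80%.

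The stated 80% is reproduced to within rounding. It concerns blood markers against MRI markers.

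**2. Information kept by a split.** Cutting a normal outcome so that a share p lies on one side multiplies the correlation by f = φ(z_p)/√(p(1 − p)). The share of information kept is about f².

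- 50:50: f = 0.399/0.5 = 0.798; f² = 0.64, so 50 participants carry the information of about 32.
- 20:80: f = 0.280/0.4 = 0.700; f² = 0.49, or about 25 of 50.

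Putting r·f into the Fisher formula at N = 50 gives r = 0.303 and 57% power for 50:50, and r = 0.266 and 46% for 20:80.

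**3. Simulation with the tests that would be used** (20,000 runs). The ordinal analysis is Spearman on a seven-level outcome with equal shares; a skewed eight-level version gives the same result to within 0.1 point. The binary analysis is the Mann-Whitney test, which is the test of AUC = 0.5. Entries are power in percent.

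| N | r | Ordinal | 50:50 | 30:70 | 20:80 | 10:90 |
|---|---|---|---|---|---|---|
| 50 | 0.38 | 73 | 56 | 51 | 44 | 31 |
| 50 | 0.45 | 88 | 73 | 68 | 60 | 43 |
| 50 | 0.50 | 94 | 82 | 77 | 69 | 51 |
| 40 | 0.38 | 62 | 46 | 42 | 37 | 25 |

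Loss against the ordinal analysis, from the unrounded figures:

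- N = 50, r = 0.38: 72.8 − 56.0 = 17 points at 50:50; 72.8 − 44.2 = 29 at 20:80; 72.8 − 30.7 = 42 at 10:90.
- N = 50, r = 0.50: 93.8 − 82.2 = 12 points at 50:50; 93.8 − 69.2 = 25 at 20:80.

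**4. Stronger association.** With an assumed GOSE distribution that puts 38% at level 4 or below, N = 50 and a cut there, r = 0.60 gives about 99% ordinal against about 95% binary, a loss of roughly 5 points. At r = 0.70 it is 100% against 99%. The loss at a near-central cut therefore fades as the association strengthens.

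**The case against.** The strongest reply is that no split is written anywhere. Section 7.3 refers only to outcomes in general, and the choice of outcome and cut is detail that an analysis plan not shown here may hold. That stands: the absence of a cut is not the point, and a reader should not infer that the protocol commits to splitting the GOSE, the FSE and every other score. What remains is that the named methods ordinarily need two classes.

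Second, 0.38 is the effect for blood markers against MRI markers. A reader might infer that the plan has less power than it claims for marker against outcome. The documents do not support this: no power is claimed for the AUC or the logistic models, and the one stated power figure is reproduced. The loss is conditional on an assumed r and split, so a general loss of 15 to 30 points cannot be asserted; at r = 0.50 and a median split it is 12.

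Third, the stated purpose is discrimination, estimated with an interval in exploratory work, and the AUC fits it. That also stands, and is why the AUC should be supplemented and not replaced.

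Two further readings go too far. The threshold of GOSE below 8 in section 4.2 is eligibility background, so losses at that cut are not losses the plan has incurred. The statement that there is no multiplicity adjustment follows the Pearson analysis and is justified by the unknown time-course of the markers, so it is not a licence to try several cuts of several outcomes.

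**Conclusion.** The point holds as an avoidable weakness in the choice of method, not as an error in a stated figure. Any two-class use of the GOSE or FSE would discard roughly a third of the information at a median split and half at 20:80 on a normal latent scale. If the marker-outcome correlation were about 0.38, that would cost about 17 to 29 points of power at N = 50 for splits from 50:50 to 20:80. For a strong association and a central cut the cost is small. The protocol gives neither the marker-outcome effect nor the outcome distribution, so the actual loss cannot be fixed more closely. A full-scale analysis is worth adding because the data are already being collected.

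**What to change.** In section 7.3, add a full-scale marker-outcome analysis alongside the AUC:

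- For the 3-month GOSE and FSE total, fit a proportional-odds model or use a rank-based analysis, with death as the worst level.
- Report an ordinal c-index with a 95% confidence interval.
- Judge an added marker by a likelihood-ratio test between models with and without it.
- Keep the binary ROC/AUC, and the change in AUC, as the discrimination summary at one cut named in advance.

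The cost is a few sentences and slightly more analysis, with no new data, visits or participants. The ordinal c-index is less familiar than an AUC and answers a somewhat different question, which is another reason to keep both. With 40 to 50 participants the proportional-odds assumption can be checked only weakly; sparse levels should be merged, or the rank-based version used.
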